8.1. General Administrative Procedures

8.1.1. Informed Consent

The investigator or qualified designee (consistent with local requirements) must obtain documented consent from each potential participant/legal representative prior to participation in this study. A signed copy of the ICF should be given to the participant and the original should be placed in the participant's medical records.

8.1.2. Assignment of Participant Number

Each participant who signs the ICF will be assigned a unique number by IRT at Screening that will identify the participant throughout the study. Once a number has been assigned, it cannot be reassigned to another study participant.

8.1.3. Medical History

A medical history will be obtained by the investigator or a medically qualified designee (consistent with local regulations) during the Screening Period and updated at the Baseline Visit. All active conditions should be recorded as well as any condition diagnosed within the participant's lifetime that the investigator deems clinically significant.

Medical history information will include, but is not limited to, symptoms of PD (current and past, including symptoms experienced prior to any PD treatment); history and treatment (if any) of cardiovascular, pulmonary, gastrointestinal, hepatic, renal, immunologic, neurologic, or psychiatric disease; reproductive status; current contraceptive method; confirmation of relevant inclusion and exclusion criteria; and any events that occur during the Screening Period and prior to the participant's first dose of study intervention (see [Appendix 4](#)).

8.1.4. Medication Review (Prior and Concomitant Medications)

The investigator or medically qualified designee should review the participant's prior medication use within 30 days. Medication that is required to be washed out prior to the study should also be recorded. All medication(s) currently taken by the participant, as well as all concomitant medication(s) taken during the study, should be recorded (see [Section 6.8](#)).

Additional information related to any medications taken for the treatment of PD and/or other treatments specific for tremor (eg, propranolol, primidone) since diagnosis should also be collected.

8.1.5. Inclusion and Exclusion Criteria Review

All inclusion and exclusion criteria should be reviewed by the investigator to ensure the participant qualifies for the study.

A Participant Eligibility Form will be completed for all participants considered by the investigator to meet the eligibility requirements at Screening. The site will submit the form to the Medical Monitor for review. The Medical Monitor will provide approval of eligibility to proceed

to the Baseline Visit. Some inclusion and exclusion criteria must be re-assessed at the Baseline Visit by the investigator or designated study site staff to confirm eligibility prior to randomization (see [Section 5](#)).

8.1.6. Timing of Study Intervention Dosing

Participants will be instructed to take a single oral daily dose of study intervention [REDACTED]

[REDACTED]. Participants should also take their daily dose of PD medication(s) at the clinic, if necessary, to ensure assessments of efficacy can occur during “ON” periods (as determined by the investigator).

At clinic visits, a light breakfast, lunch, or snack will be provided as needed. Participants will be asked to fast for their Screening Visit only.

8.1.7. Montreal Cognitive Assessment

The MoCA is designed as a rapid screening instrument to detect mild cognitive dysfunction. The MoCA test was validated in 2000 and revalidated in 2004 ([Nasreddine, 2005](#)). The assessment comprises a 30-question test that can be completed in approximately 10 minutes. The MoCA assesses different cognitive domains including attention and concentration, executive functions, memory, language, visuoconstructional skills, conceptual thinking, calculations, and orientation. The total possible score is 30 points; a score of 26 or above is considered normal.

A sample MoCA can be found in the Trial Site Binder.

8.2. Efficacy Assessments

Planned time points for all efficacy assessments are provided in the SoA ([Section 1.3](#)).

On clinic visit days, site staff will record the time of the participant’s dose of study intervention as well as the time of the last dose(s) of PD medication(s) prior to the efficacy assessments. For all participants, assessment of efficacy should occur during “ON” periods, as determined by the investigator, in relation to the participant’s PD medication(s).

Note that the primary endpoint is the TETRAS composite outcome score. First published in 2008 and designed as a 10-minute clinical assessment of tremor ([Elble, 2008; Elble, 2012](#)), the TETRAS consists of a 12-item ADL subscale and a 9-item PS. The TETRAS composite score utilized in the present study is comprised of the sum of modified items 1 to 11 of the TETRAS-ADL subscale (see [Section 8.2.1](#)) and modified items 6 (6a and 6b) and 7 of the TETRAS-PS (see [Section 8.2.2](#)). While the TETRAS has not been validated in a PD population, many of the ADL and functional tasks assessed by the composite outcome score have been shown to be impacted by tremor in PD ([Elble, 2016; Louis and Machado, 2015](#)).

8.2.1. Tremor Research Group Essential Tremor Rating Assessment Scale – Activities of Daily Living

The TETRAS-ADL subscale includes many of the items assessed in previously developed scales for the evaluation of tremor ([Fahn, 1993; Louis, 2000; Bain, 1993](#)) including eating and drinking, dressing and personal hygiene, carrying items, and finer motor skills. Each item in the

TETRAS-ADL subscale is rated on a 0 (normal activity) to 4 (severe abnormality) scale. The sum of the individual scores provides the overall score, ranging from 0 to 48. The TETRAS-ADL subscale has face validity, has preliminarily demonstrated test-retest reliability, and is highly correlated with the TETRAS-PS in the ET population (Elble, 2012; Elble, 2016). It has also demonstrated sensitivity to change with suvacecaltamide treatment in the T-CALM study in participants with ET. Items 1 to 11 of the TETRAS-ADL subscale assess the impact of tremor on day-to-day functioning, while item 12 assesses the social impact of tremor.

A sample TETRAS-ADL subscale can be found in the Trial Site Binder.

8.2.2. Tremor Research Group Essential Tremor Rating Assessment Scale – Performance Subscale

The TETRAS-PS quantifies tremor in the head, face, voice, limbs, and trunk. Each item on the TETRAS-PS is rated on a 0 to 4 rating scale, with scoring of upper limb tremor allowing for 0.5-point increments. Specific amplitude ranges (measured in centimeters) define the tremor rating. Blinded raters first estimate the maximum amplitude of tremor and then assign the corresponding rating. The sum of the individual rating scores provides the overall performance score, ranging from 0 to 64. The TETRAS-PS has demonstrated both test-retest reliability and sensitivity to change in the ET population (Elble, 2012; suvacecaltamide IB T-CALM study) and was given a “recommended” rating as a tremor severity scale by the MDS for ET (Elble, 2013).

TETRAS-PS items 6 (6a and 6b) and 7 are the Archimedes spiral and handwriting assessments, respectively.

Both are rated on a 0 (normal) to 4 (severe) rating scale. The Archimedes spiral is tested in both the right (ie, item 6a) and the left (ie, item 6b) hands, while the handwriting is assessed with the dominant hand only. The sum of the TETRAS-PS items 6 (6a and 6b) and 7 provides a score ranging from 0 to 12. The Archimedes spiral and handwriting tasks have been integral in the routine examination of patients with tremor for decades, heavily utilized in tremor rating scales beyond the TETRAS (Bain, 1993; Fahn, 1993; Louis, 2001) and have demonstrated sensitivity to change with treatment in the ET population (Calzetti, 1982; Haubenberger, 2011; Hopfner, 2015; Koller, 1986; Shill, 2004; Tolosa and Loewenson, 1975).

A sample TETRAS-PS can be found in the Trial Site Binder.

8.2.3. Clinical Global Impression of Severity

The CGI-S will be assessed by qualified personnel to assess the severity of the impact of tremor in PD on the participants’ ability to function. The CGI-S is a 5-point Likert-type rating scale and is widely used in clinical psychopharmacology trials to assess severity of illness. The responses to this investigator-completed scale range from 1 (no limitations) to 5 (severe). The investigator will rate his/her impression of the severity of the impact of tremor in PD on the participant’s current ability to function relative to his/her experience with this patient population.

A sample CGI-S can be found in the Trial Site Binder.

8.2.4. Clinical Global Impression of Change

The CGI-C is a 5-point Likert-type rating scale widely used to assess efficacy in clinical drug trials. Investigators as trained raters will rate their impression of any change in the severity of the

participant's condition since Baseline on a 5-point scale ranging from 1 (much improved) to 5 (much worse). Investigators' rating will focus on the participants' change in their ability to function due to tremor in PD.

A sample CGI-C can be found in the Trial Site Binder.

8.2.5. Patient Global Impression of Severity

The PGI-S is a 5-point Likert-type rating scale, with response options ranging from 1 (no limitations) to 5 (severe). The participant will rate his/her impression of the severity of the impact of their tremor in PD on their current ability to function.

A sample PGI-S can be found in the Trial Site Binder.

8.2.6. Patient Global Impression of Change

The PGI-C is a 5-point Likert-type rating scale and a widely used assessment to assess efficacy in clinical drug trials. Participants will rate the change in their condition since Baseline on a 5-point scale ranging from 1 (much improved) to 5 (much worse). Participants' rating will focus on the change in their ability to function due to tremor in PD.

A sample PGI-C can be found in the Trial Site Binder.

8.2.7. Movement Disorder Society Unified Parkinson's Disease Rating Scale

The MDS-UPDRS is the most widely used clinical rating scale for tracking PD progression ([Goetz, 2008](#); [Ramaker, 2002](#)). The scale takes approximately 30 minutes to complete and consists of 4 parts:

- Part I: non-motor aspects of experiences of daily living;
- Part II: motor aspects of experiences of daily living;
- Part III: motor examination; and
- Part IV: motor complications (dyskinesias and motor fluctuations including “OFF” state dystonia).

Note that the Part I, II, III, and IV scores, total score, and the tremor score (items 2.10, 3.15, 3.16, 3.17, and 3.18) will be calculated (see other secondary endpoints, [Section 3](#)).

A sample MDS-UPDRS can be found in the Trial Site Binder.

[REDACTED]

Topic	Percentage
Global warming	98
Evolution	97
Black holes	61
Big Bang theory	59
Quantum mechanics	94
Neuroscience	93
Relativity	92
String theory	91
Dark matter	90
Dark energy	89
Climate change	88
Plate tectonics	87
Big Data	86
Cloud computing	85
Artificial intelligence	84
Blockchain	83
Quantum computing	82
Neurotechnology	81
Neuroscience	80
Neurodiversity	79
Neuroethics	78
Neuroeconomics	77
Neurophilosophy	76
Neuroaesthetics	75
Neurosemantics	74
Neurophenomenology	73
Neurofunctionalism	72
Neurosymbolism	71
Neurofunctionalism	70
Neurosymbolism	69
Neurofunctionalism	68
Neurosymbolism	67
Neurofunctionalism	66
Neurosymbolism	65
Neurofunctionalism	64
Neurosymbolism	63
Neurofunctionalism	62
Neurosymbolism	61
Neurofunctionalism	60
Neurosymbolism	59
Neurofunctionalism	58
Neurosymbolism	57
Neurofunctionalism	56
Neurosymbolism	55
Neurofunctionalism	54
Neurosymbolism	53
Neurofunctionalism	52
Neurosymbolism	51
Neurofunctionalism	50
Neurosymbolism	49
Neurofunctionalism	48
Neurosymbolism	47
Neurofunctionalism	46
Neurosymbolism	45
Neurofunctionalism	44
Neurosymbolism	43
Neurofunctionalism	42
Neurosymbolism	41
Neurofunctionalism	40
Neurosymbolism	39
Neurofunctionalism	38
Neurosymbolism	37
Neurofunctionalism	36
Neurosymbolism	35
Neurofunctionalism	34
Neurosymbolism	33
Neurofunctionalism	32
Neurosymbolism	31
Neurofunctionalism	30
Neurosymbolism	29
Neurofunctionalism	28
Neurosymbolism	27
Neurofunctionalism	26
Neurosymbolism	25
Neurofunctionalism	24
Neurosymbolism	23
Neurofunctionalism	22
Neurosymbolism	21
Neurofunctionalism	20
Neurosymbolism	19
Neurofunctionalism	18
Neurosymbolism	17
Neurofunctionalism	16
Neurosymbolism	15
Neurofunctionalism	14
Neurosymbolism	13
Neurofunctionalism	12
Neurosymbolism	11
Neurofunctionalism	10
Neurosymbolism	9
Neurofunctionalism	8
Neurosymbolism	7
Neurofunctionalism	6
Neurosymbolism	5
Neurofunctionalism	4
Neurosymbolism	3
Neurofunctionalism	2
Neurosymbolism	1
Neurofunctionalism	0

8.3. Safety Assessments

Planned time points for all safety assessments are provided in the SoA ([Section 1.3](#)).

8.3.1. Physical Examinations

- A complete physical examination will include, at a minimum, assessments of the cardiovascular, respiratory, gastrointestinal, and neurological systems; a genitourinary exam is excluded. Height and weight (in ordinary indoor clothes without shoes) will also be measured and recorded as indicated in the SoA.

- Investigators should pay special attention to clinical signs related to previous clinically significant or serious illnesses.
 - Any abnormalities identified at the Screening Visit physical exam should be recorded as medical history.

8.3.2. Vital Signs

- Vital signs (to be taken prior to blood collection, when possible) including oral temperature, pulse rate, respiratory rate, and orthostatic blood pressure (systolic and diastolic) will be assessed at each clinic visit as indicated in the SoA.
- Blood pressure and pulse measurements will be assessed with a completely automated device. Manual techniques will be used only if an automated device is not available.
- Orthostatic blood pressure (systolic and diastolic) and pulse rate will be obtained after the participant has been in the supine position for at least 5 minutes, and again in the standing position after the participant has been standing for 2 minutes. At Screening and Baseline, orthostatic assessments will be taken in triplicate (at intervals of 15 to 30 minutes). All 3 measurements should be recorded. The average of the 3 measurements will be automatically calculated. At all other visits, orthostatic blood pressure and pulse assessments will consist of a single post-dose measurement.
- Respiratory rate and body temperature will be assessed after the participant has been resting and seated (or supine) for at least 5 minutes.

8.3.3. Electrocardiograms

- [REDACTED] will be obtained as outlined in the SoA using an ECG machine that automatically calculates the heart rate and measures PR, QRS, QT, and corrected QT (ie, QTc), QTcF intervals.
- [REDACTED]
- Each ECG will be reviewed, initially interpreted, signed, and dated by the investigator or a designated physician after collection. All ECGs (except for ECGs for participants who are screen failures) will be transmitted to a designated central ECG laboratory. A cardiologist at the central ECG laboratory will conduct a full over-read. A report based on data from this over-read will be issued to the site.
- Additional ECGs may be obtained at any time per the investigator's judgement.

8.3.4. Clinical Safety Laboratory Assessments

- See [Appendix 3](#) for the list of clinical laboratory tests to be performed and to the SoA for the timing and frequency.
 - Screening laboratory assessments should be conducted under fasting conditions. Record if the participant was fasting or non-fasting.

- Screening laboratory assessments (including urinalysis) should be repeated at the Baseline Visit if the visit occurs outside of the Screening Period.
- The investigator must review the laboratory report, document this review, and record any markedly abnormal changes occurring during the study as an AE. Laboratory reports must be filed with the source documents. Note: any markedly abnormal laboratory findings or other abnormal safety assessments that are associated with a specific diagnosis would not be reported as an AE. (The specific diagnosis would be reported as an AE if the event occurred after the participant received his/her first dose of study intervention; see [Appendix 4](#).)
- Laboratory findings associated with the underlying disease are not considered markedly abnormal unless judged by the investigator to be more severe than expected for the participant's condition.
- All laboratory tests with markedly abnormal values during participation in the study and considered by the investigator to be related to study intervention should be repeated until the values return to normal or baseline or are no longer considered markedly abnormal by the investigator or Medical Monitor.
 - If markedly abnormal values do not return to normal/baseline within a period judged reasonable by the investigator, the etiology should be identified, and the sponsor notified.
 - All protocol-required laboratory tests, as defined in [Appendix 3](#), must be conducted in accordance with the Laboratory Manual and the SoA.

8.3.5. Pregnancy Testing

Pregnancy testing is applicable only for WOCBP.

- Refer to [Section 5.1](#) for pregnancy testing entry criteria.
- Pregnancy testing (urine or serum as required by local regulations) should be conducted as outlined in the SoA.
 - In the event of a positive urine pregnancy test, confirmatory serum pregnancy test must be conducted.
- Additional serum or urine pregnancy tests may be performed, as determined by the investigator or required by local regulation, to establish the absence of pregnancy at any time during the participant's participation in the study, and in addition to laboratory testing, the investigator must take appropriate steps to confirm, evaluate, and manage the potential pregnancy, including referral, when indicated.

8.3.6. Suicidal Ideation and Behavior Risk Monitoring

Suvecaltamide is considered a CNS-active study intervention. Participants being treated with suvecaltamide should be monitored appropriately and observed closely for suicidal ideation and behavior or any other unusual changes in behavior, especially at the beginning and end of the course of intervention, or at the time of dose changes (increases or decreases). Participants who experience signs of suicidal ideation or behavior should undergo a risk assessment. All factors

contributing to suicidal ideation or behavior should be evaluated and consideration should be given to discontinuation of the study intervention.

Baseline assessment of suicidal ideation and behavior/intervention emergent suicidal ideation and behavior will be monitored during the study using the C SSRS administered by a qualified and appropriately trained rater. At the Screening Visit, the Screening/Baseline Version of the C SSRS will be administered to participants to exclude any individual with active suicidal ideation or behavior.

The Since Last Visit Version of the C-SSRS will be administered to participants at every clinic visit after their Screening Visit, including the Baseline Visit. At the Baseline Visit, any participant who reports active suicidal ideation (eg, a positive response to Question 4 or 5 on the C-SSRS) or behavior (eg, a positive response to any suicidal behavior question on the C-SSRS) will be excluded. At postbaseline visits, active suicidal ideation (eg, a positive response to Question 4 or 5 on the C-SSRS) or behavior (eg, a positive response to any suicidal behavior question on the C-SSRS) must be recorded as an AE and reported to the sponsor or designee within 24 hours of first knowledge of the event by study personnel. Please refer to [Appendix 4](#) for details.

8.3.7. Questionnaire for Impulsive-Compulsive Disorders in Parkinson's Disease Rating Scale

The QUIP-RS is a rating scale designed to measure the severity of, and support a diagnosis of, impulse control and related disorders in PD. It can also be used to monitor changes in symptom severity over time ([Weintraub, 2012](#)).

The QUIP-RS is a brief, self-rated questionnaire. It consists of 4 primary questions (pertaining to commonly reported thoughts, urges/desires, and behaviors associated with ICDs), each applied to the 4 ICDs (gambling, sex, buying, and eating) and 3 related disorders (hobbyism, punding, and medication use). It uses a 5-point Likert scale (scored 0 [never] to 4 [very often] for each question) to gauge the frequency of behaviors.

A copy of the QUIP-RS is found in the Trial Site Binder.

8.4. Adverse Events, Serious Adverse Events, and Other Safety Reporting

The definitions of AEs and SAEs can be found in [Appendix 4](#).

Adverse events will be reported by the participant (or, when appropriate, by a caregiver, surrogate, or the participant's legally authorized representative).

The investigator and any qualified designees are responsible for detecting, documenting, and recording events that meet the definition of an AE or SAE and remain responsible for following up all AEs (see [Section 8.4.3](#)).

The method of recording, evaluating, and assessing causality of AEs and SAEs and the procedures for completing and transmitting SAE reports are provided in [Appendix 4](#).

8.4.1. Time Period and Frequency for Collecting Adverse Event and Serious Adverse Event Information

All AEs and SAEs will be collected from the start of intervention until the Safety Follow-up Visit at the time points specified in the SoA ([Section 1.3](#)).

Note: All SAEs that occur after the ICF is signed but before study intervention/treatment must be reported by the investigator if they cause the participant to be excluded from the study or if they are the result of a protocol-specified intervention, including but not limited to washout or discontinuation of usual therapy, diet, placebo treatment, or a procedure.

Medical occurrences that begin before the start of study intervention but after obtaining informed consent will be recorded as Medical History/Current Medical Conditions, not as AEs.

All SAEs will be recorded and reported to the sponsor or designee within 24 hours of first knowledge of the event by study personnel, as indicated in [Appendix 4](#). The investigator will submit any updated SAE data to the sponsor within 24 hours of it being available.

Investigators are not obligated to actively seek information on AEs or SAEs after conclusion of the study participation. However, if the investigator learns of any SAE, including a death, at any time after a participant has been discharged from the study, and he/she considers the event to be reasonably related to the study intervention or study participation, the investigator should promptly notify the sponsor.

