1.3. Schedule of Activities

Table 4: Schedule of Activities

	Screening (up to 28 days)	BL	Dose Titration and Optimization Period			Maintenance Period						Efficacy FU Visit ^a	E/D Visit ^b	Safety FU Period	Comments
	SV	BL	W1, W2	W3, W4	W5	W6, W7, W8	W9	W10, W11, W12	W13	W14, W15, W16	W17			W19	See Section 7 regarding d/c of study intervention and participant d/c or withdrawal.
Clinic Visits ^c	X	X	X ^d		X ^d		X ^d		X ^d		X	X ^d	X	X ^{b, d}	
Phone Visits ^c				X		X		X		X					
Day	-28 to -3	-1	7, 14	21, 28	35	42, 49, 56	63	70, 77, 84	91	98, 105, 112	119			133	
			(-1, +2)			(-3, +2)									Visit windows
ICF	X														
Randomization		X													
I/E criteria	X	X													See Section 5.
Demographics	X														
Medical history	X	X													See Section 8.1.3 and Section 8.4.1.
Complete physical exam	X										X		X	X	See Section 8.3.1.
Height	X														See Section 8.3.1.
Weight	X	X									X		X	X	See Section 8.3.1.
Serum or urine pregnancy test	X														See Section 8.3.5.
Urine pregnancy test ^c		X			X	X		X		X		X	X		See Section 8.3.5
Urine drug screen	X	X			X	X		X		X		X			See Section 7.1.2 and Appendix 3.

	Screening (up to 28 days)	BL	Dose Titration and Optimization Period			Maintenance Period						Efficacy FU Visit ^a	E/D Visit ^b	Safety FU Period	Comments
	SV	BL	W1, W2	W3, W4	W5	W6, W7, W8	W9	W10, W11, W12	W13	W14, W15, W16	W17			W19	See Section 7 regarding d/c of study intervention and participant d/c or withdrawal.
Clinic Visits ^c	X	X	X ^d		X ^d		X ^d		X ^d		X	X ^d	X	X ^{b, d}	
Phone Visits ^c				X		X		X		X					
Day	-28 to -3	-1	7, 14	21, 28	35	42, 49, 56	63	70, 77, 84	91	98, 105, 112	119			133	
			(-1, +2)			(-3, +2)									Visit windows
Breath alcohol test	X	X			X		X		X		X		X		See Section 7.1.2 .
Laboratory assessments (chemistry, hematology)	X	X			X		X		X		X		X	X	See Section 8.3.4 and Appendix 3 .
Orthostatic blood pressure and pulse	X	X	X		X		X		X		X		X	X	See Section 8.3.2 .
Urinalysis	X	X			X		X		X		X		X	X	See Section 8.3.4 and Appendix 3 .
Temperature and respiratory rate	X	X	W1 only		X		X		X		X		X	X	See Section 8.3.2 .
12-lead ECG	X	X	W1 only				X				X		X	X	See Section 8.3.3 .
C-SSRS Screening/ Baseline Version	X														See Section 8.3.6 .
C-SSRS Since Last Visit Version		X	X		X		X		X		X	X	X	X	See Section 8.3.6 .

	Screening (up to 28 days)	BL	Dose Titration and Optimization Period			Maintenance Period						Efficacy FU Visit ^a	E/D Visit ^b	Safety FU Period	Comments

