7.1.1. Participants Remaining in the Study After Study Intervention Discontinuation

Discontinuation from study intervention does not represent discontinuation from the study. For participants who discontinue study intervention early, every effort should be made to attend Efficacy Follow-up Visits through 17 weeks after the first dose of study intervention. After completing the E/D visit, if the participant is willing to attend Efficacy Follow-up Visits after the study intervention is discontinued, the guidelines for scheduling efficacy visits are as follows:

- For participants who discontinue study intervention prior to the Week 9 Visit, it is encouraged to schedule 3 additional Efficacy Follow-up Visits at 9, 13, and 17 weeks after first dose.
- For participants who discontinue study intervention after the Week 9 Visit but prior to the Week 13 visit, it is encouraged to schedule 2 additional Efficacy Follow-up Visits at 13 and 17 weeks after first dose.
- For participants who discontinue study intervention after the Week 13 Visit but prior to the Week 17 Visit, it is encouraged to schedule an additional Efficacy Follow-up Visit at 17 weeks after first dose.
- Participants should be scheduled for the Safety Follow-up Visit 2 weeks after the last dose of study intervention. However, 1 of the Efficacy Follow-up Visits can be combined with the participant's Safety Follow-up Visit if the Efficacy Follow-up Visit is scheduled to occur within 2 weeks after the participant's last dose of study intervention.

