#### **Derivations and Definitions:**

AEs will be collected and reported from the start of study treatment up to the Safety Follow-up visit (approximately 14 days after the last dose of study treatment).

A treatment-emergent adverse event (TEAE) is defined as any AE that began on or after the first dose of study treatment until up to 14 days after the last dose of study treatment.

Adverse events of special interest (AESI) are AEs that are of scientific and medical concern specific to JZP385, which includes hallucination, and syncope. The groupings are defined using MedDRA terms, SMQs (standardized MedDRA queries) and PTs.

Time of first onset of AE is calculated as: TEAE start date – First dose date + 1 and is categorized as:

- Week 1 and 2 ( $1 \leq \text{day of first onset of AE} \leq 14$ )
- Week 3 ( $15 \leq \text{day of first onset of AE} \leq 21$ )
- Week 4 ( $22 \leq \text{day of first onset of AE} \leq 28$ )
- Week 5 ( $29 \leq \text{day of first onset of AE} \leq 35$ )
- Weeks 6 – 17 ( $36 \leq \text{day of first onset of AE} \leq 119$ )
- > Week 17 ( $120 \leq \text{day of first onset of AE}$ )

Incomplete AE start/stop date will be imputed according to Section 6.1.

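### Scheduled AE and SAE collection ends at the Safety Follow-up Visit, although early discontinuers may stay in the study with C-SSRS through Week 17; suicidality found after that visit must be recorded under 8.3.6 but lies outside the 8.4.1 window, and 8.4.1 is unclear on other SAEs

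*Protocol*

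**What the plan says.** **Collection window.** Protocol 8.4.1: "All AEs and SAEs will be collected from the start of intervention until the Safety Follow-up Visit". SAP 4.6.2 repeats this end point and puts it at roughly 14 days after the last dose. Its TEAE definition reads: "any AE that began on or after the first dose of study treatment until up to 14 days after the last dose of study treatment".

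**Who stays in the study.** Protocol 7.1.1 separates stopping study intervention from leaving the study. For those who stop, "every effort should be made to attend Efficacy Follow-up Visits through 17 weeks after the first dose of study intervention". Depending on when they stop, visits are encouraged at Weeks 9, 13 and 17. On the closing visit: "Participants should be scheduled for the Safety Follow-up Visit 2 weeks after the last dose of study intervention". An Efficacy Follow-up Visit that falls within those 2 weeks may be combined with it.

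**What is done at Efficacy Follow-up.** In the Schedule of Activities (Protocol 1.3, Table 4), the row "C-SSRS Since Last Visit Version" and the concomitant-medication row are both marked under Efficacy FU. The AE row is marked at E/D and Safety FU, with no mark under Efficacy FU.

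**Suicidality.** Protocol 8.3.6 requires that active ideation or behavior at postbaseline visits "must be recorded as an AE and reported to the sponsor or designee within 24 hours of first knowledge of the event". It sets no end date.

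**SAEs.** Three further statements in 8.4.1 matter. SAEs go to the sponsor within 24 hours of staff learning of them, with no end date stated. The duty to look actively for events lapses once study participation has concluded. A late SAE learned of "at any time after a participant has been discharged from the study" is to be notified if the investigator considers it reasonably related.

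**The concern.** The period in which participants are assessed and the period in which adverse events are collected do not match. A participant who stops early can pass the Safety Follow-up Visit and still return for up to three Efficacy Follow-up Visits. At each one the site asks about suicidality and medication, but no AE inquiry is scheduled.

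This has two consequences. First, for the same C-SSRS finding, 8.3.6 tells the site to create an AE record, while 8.4.1 and the Schedule have already closed the collection period. Second, the plan schedules no collection of any other AE in that interval and leaves the status of SAEs to interpretation.

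The Week 17 scores of these participants enter the main treatment-policy analysis. A hospitalization, fall or psychiatric event that helps explain such a score may not have been asked about. Protocol 8.3.6 also describes the drug as CNS-active and asks for close observation around the end of the course of intervention.

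**Working it through.** The plan gives no figure for this point. The check is a comparison of passages followed by a day count.

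**Step 1: a positive C-SSRS at an Efficacy Follow-up Visit after the Safety Follow-up Visit.**
- 8.3.6: it is a postbaseline visit, so an AE record and a 24-hour report are required.
- 8.4.1 and SAP 4.6.2: the AE collection period has ended.
- Schedule: C-SSRS marked, AE not marked.

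The requirement and the window conflict.

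**Step 2: another SAE in the same interval.**
- The opening sentence of 8.4.1 puts it outside the collection period.
- The 24-hour sentence has no end date and would cover an SAE that staff learn of.
- Active seeking is lifted only after participation concludes, which has not yet happened.
- The post-discharge clause does not fit, because the participant is still in the study.
- No scheduled inquiry would bring the event to light.

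Two readings are defensible, so the text is ambiguous.

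**Step 3: length of the interval.** Inputs are the Week 17 visit on Day 119 (Schedule) and the Safety Follow-up Visit 14 days after the last dose (7.1.1). For a participant followed to Day 119:

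interval = max(0, 119 − (last-dose day + 14))

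| Last dose | Safety FU | Interval (days) | Efficacy FU Visits after Safety FU |
|---|---|---|---|
| Day 14 | Day 28 | 119 − 28 = 91 | Weeks 9, 13, 17 |
| Day 28 | Day 42 | 119 − 42 = 77 | Weeks 9, 13, 17 |
| Day 56 | Day 70 | 119 − 70 = 49 | Weeks 13, 17 |
| Day 84 | Day 98 | 119 − 98 = 21 | Week 17 |
| Day 105 | Day 119 | 119 − 119 = 0 | none |

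The Efficacy Follow-up Visits fall on Days 63, 91 and 119. All three come after the Safety Follow-up Visit when last-dose day + 14 < 63, that is, for a last dose before Day 49. With a last dose on Day 49, the Week 9 visit coincides with the Safety Follow-up Visit and is covered.

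**Step 4: sensitivity to the anchor.** Schedule footnote b times the Safety Follow-up Visit from the E/D Visit, whereas 7.1.1 times it from the last dose. Under the footnote, each interval shortens by the days between last dose and E/D Visit. The two anchors should be reconciled, but the conclusion does not depend on which applies.

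**The case against.** The strongest reply is that the SAE provisions already reach this interval. The 24-hour requirement in 8.4.1 is open-ended, Appendix 4 repeats it, and active seeking continues until participation concludes. This stands far enough to rule out a reading that a reader might infer, that SAEs after the Safety Follow-up Visit are not collected. It does not settle the matter. The 24-hour sentence governs speed of reporting, the opening sentence governs the period, and the same section separately restricts pre-dose and post-discharge SAEs, which would be needless if the sentence had no time limit.

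Second, 8.3.6 is the specific rule and 8.4.1 does not forbid a record that another section requires. A careful site would probably record the event, and C-SSRS results are also summarized and listed in their own right (SAP 4.6.3.5). That reduces the practical harm but leaves the two sections inconsistent.

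Third, the SAP already lists all AEs and serious AEs, and summarizes and lists deaths, without limiting them to TEAEs. This is correct, so no new listing is needed. A listing can show only what was collected, however.

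Fourth, the missing AE mark is read from a table extracted from PDF, in which some rows look misaligned and the span of the AE arrow is lost. The concomitant-medication row, with three marks where the AE row has two, supports the reading but does not prove it. The 8.4.1 wording carries the point without it.

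Finally, attendance is encouraged rather than assured, combined visits are covered, and concomitant medications are recorded with a reason for use, so treated events may leave a trace. All of this limits the scope.

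**Conclusion.** The point holds as an inconsistency with a real effect on data capture. Scheduled AE and SAE collection ends before some participants finish the study, 8.3.6 demands a record outside that period, and 8.4.1 is ambiguous about SAEs within it. The interval is 91 days for a last dose on Day 14 and 49 days for Day 56, and there is none from Day 105. These figures assume follow-up to Day 119 and a Safety Follow-up Visit 14 days after the last dose.

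The documents do not give the number affected. A reader might take the 20% drop-out assumption, 0.20 × 160 = 32, as an upper limit. It is not one: Protocol Table 3 sets 160 randomized against 128 completing Week 17 assessments, so the 32 are those who do not complete them. Someone who stops treatment but attends at Week 17 counts among the 128.

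A reader might also infer bias in the between-arm TEAE comparison. The documents do not support that. The TEAE definition closes 14 days after the last dose in both arms, so later events lie outside those tables whether or not they are collected. What is at stake is the record of later events in participants whose efficacy data are still being used.

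**What to change.** Reconcile Protocol 8.4.1, 8.3.6, the Schedule and SAP 4.6.2:

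1. In 8.4.1, collect AEs and SAEs until the later of the Safety Follow-up Visit and the last Efficacy Follow-up Visit.
2. Add the AE mark under Efficacy FU in Table 4.
3. Align the collection sentence in SAP 4.6.2 with the new end point and keep the 14-day TEAE definition.
4. In the existing all-AE and serious-AE listings, flag events that start more than 14 days after the last dose, including those triggered by the C-SSRS.

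The cost is a wording change in the protocol and the SAP, one Schedule cell and one listing flag. The visits already take place, with C-SSRS and medication review. The downside is a few more AE records, some of them unrelated to the drug.
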